**Population:**

**750 total with comorbidity overlap (250 HFrEF, 250 HFpEF, 500 AF, 250 T2D/ASVD)**

*Inclusion criteria:*

1. Age  $\geq 18$  years
2. Personal access to a computer and/or smartphone for app download
3. Heart Failure (reduced and preserved ejection fraction) AND/OR
4. Atrial Fibrillation with CHA2DS2-VASc score greater than or equal to 2 in men and greater than or equal to 3 in women AND/OR
5. T2D and ASCVD, defined as follows:
  - a. Known CAD, prior ACS, or coronary artery revascularization
  - b. Prior TIA/stroke or known carotid or intracerebral atherosclerosis
  - c. Prior PAD including requiring revascularization

*Exclusion criteria:*

- All patients
  - Current or anticipated participation in an interventional clinical trial of a drug/device
  - Currently receiving comfort care or enrolled in hospice
  - Life expectancy <1 year
  - Pregnancy or active breastfeeding
  - Current or anticipated participation in an interventional clinical trial (other than TRANSFORM GDMT)
  - Patients without a clinical encounter within three years of study start date
- Heart Failure patients:
  - History of or plan for heart transplantation or left ventricular assist device
  - Palliative chronic inotropic therapy
  - NYHA Class 4 heart failure
- Atrial Fibrillation patients:
  - Current prescription for OAC
  - Reversible cause of atrial fibrillation, such as post-cardiothoracic surgery or thyrotoxicosis
  - History of ischemic stroke in prior 7 days
  - Transient ischemic attack in prior 3 days
  - Platelet count <70,000/ml
  - Hemoglobin concentration <8g/dl
  - History of or condition associated with increased bleeding risk, such as hemophilia
  - History of mechanical valve replacement
  - Major surgical procedure or trauma within 14 days
  - Clinically significant gastrointestinal bleeding within 8 weeks

- History of intracranial, intraocular, spinal, or atraumatic intra-articular bleeding
- T2D/ASCVD patients with or without HF or AF:
  - Current prescription for SGLT2i and GLP-1RA
  - Current or planned hemodialysis
  - Decompensated end stage liver disease
  - Type 1 diabetes
  - Prior diabetic ketoacidosis
  - Gestational diabetes
  - History of pancreatitis or pancreatic cancer

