### **Subanalysis for each disease state:**

T2D/ASCVD:

- a. the proportion of treatment-naïve patients who are newly prescribed a SGLT2i and/or GLP-1RA over 9-months
- b. Rate of medication persistence: % of patients on a SGLT2i and/or GLP-1RA at baseline who remained on a SGLT2i and/or GLP-1RA during the study period

HFrEF: For those with HFrEF, baseline to 9 months change in average composite endpoint of at least 50% target dose achievement for the main classes of drugs (RASi/beta blockers/MRA/SGLT2i) among eligible patients.

- a. Goal doses will be based on the 2020 ACC Expert Consensus Decision Pathway for Optimization of Heart Failure Treatment (4).
- b. To calculate this composite:
  - i. Numerator = receiving ARNI/ACEI/ARB at 50% or higher of target dose + receiving evidence-based beta blocker at 50% or higher of target dose + receiving MRA at 50% or higher of target dose + receiving SGLT2i at 50% or higher of target dose.
  - ii. Denominator = eligible to receive ARNI/ACEI/ARB, eligible to receive evidence-based beta blocker, and eligible to receive MRA, and eligible to receive SGLT2i.
  - iii. Using this approach, each patient may contribute to the numerator or be in the denominator 1, 2, 3 or 4 times, depending on meeting criteria and if eligible in that domain. An advantage of this composite approach is that it allows for a holistic view of all classes of drugs considered and allows for assessment not only of up-titration but also down-titration as well.
- c. Rate of medication persistence: % of patients on medications at baseline who remained on medications during the study period

Page Break

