**The final Statistical Analysis Plan (SAP) will be finalized prior to the study completion.**

**Patient-Level Randomization to 3 Quality Improvement Initiative:** Simple (traditional) randomization minimizes variation in clinical profiles of patients included in each arm. While cluster randomization at the clinician level may limit the potential for contamination bias (chance that clinicians caring for patients randomized to one implementation approach may influence the care of another patient on their panel), the number of eligible patients under each individual clinician's care is anticipated to be small.

**Power Estimates:** In this 3-arm trial, stratified by study site, we estimated the sample size of patients needed to show a difference between the quality improvement arms.

Current estimates of use of either SGLT2i or GLP-1RA among eligible patients is 15%. Assuming an alpha of 0.05, we would require 121 patients in each of the 3 arms to show 80% power to detect at least an absolute difference of 15% between education alone and the education + decision support arms and a 15% between education alone and the education + decision support + facilitated referral group. Assuming a 20-25% loss to follow-up rate, 750 patients would be required.

Current estimates of optimal GDMT prescription and titration for HFrEF are 2%. The differences for each arm are expected to be greater than the SGLT2i or GLP-1RA classes.

Given the evolving evidence for HFpEF, there are no established rates for GDMT.

Current estimates of optimal use of anticoagulation medication for AF is 60-65%. The study does not anticipate reaching power for this disease state.

The primary comparison will be between the education alone arm (1) and the education + decision support + referral group (3). Secondary analyses will compare education alone (1) with the education + decision support group (2). The study will be powered for both primary and secondary comparisons for T2D/ASCVD and HF (HFrEF and HFpEF combined).

Rates of Primary Endpoint Over 9 months			Estimated Number of Patients in Each of 3 Arms			
Education Alone (1)	Education +Decision Support (2)	Education+Decision+Referral Support (3)	80% power		90% power	
			1 vs 2	1 vs 3	1 vs 2	1 vs 3
0.05	0.075	0.1	1471	435	1969	582
0.1	0.15	0.2	686	199	918	266
0.125	0.1875	0.25	529	152	708	203
0.15	0.3	0.3	424	121	568	161

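### The protocol claims adequate power for T2D/ASCVD, but its 250 such patients give about 83 per arm (63 to 67 after the stated loss) against the 121 required, so power is about 52 to 55%, not 80%.

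*Protocol*

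**What the plan says.** All of the power statements are in the protocol's Statistical Methods section, under Power Estimates.

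- **Control rate:** "Current estimates of use of either SGLT2i or GLP-1RA among eligible patients is 15" per cent.
- **Effect:** the aim is "to detect at least an absolute difference of 15% between education alone and the education + decision support arms", with the same difference for education alone against the arm that adds referral.
- **Error rate and size:** "Assuming an alpha of 0.05", "we would require 121 patients in each of the 3 arms to show 80% power".
- **Total:** "Assuming a 20-25% loss to follow-up rate, 750 patients would be required".
- **Claim by disease state:** "The study will be powered for both primary and secondary comparisons for T2D/ASCVD and HF (HFrEF and HFpEF combined"). The primary comparison is arm 1 against arm 3, and the secondary is arm 1 against arm 2. Lack of power is conceded for AF only.

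The Population list under Study Design (and the Patient Recruitment table) sets the numbers: "750 total with comorbidity overlap (250 HFrEF, 250 HFpEF, 500 AF, 250 T2D/ASVD"). The Randomization Scheme under Research Methods allocates 1:1:1. The matching endpoint, under Subanalysis for each disease state, is "the proportion of treatment-naïve patients who are newly prescribed a SGLT2i and/or GLP-1RA over 9-months".

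**The concern.** The calculation uses an outcome that belongs to the T2D/ASCVD cohort, and the text then says the trial is powered for that cohort. Yet the cohort is planned at 250 over three arms, fewer than the 363 the calculation needs even if nobody is lost. The 750 given as the result is the headcount over all disease states, and the T2D/ASCVD cohort is a third of it.

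T2D/ASCVD is the only disease state with a worked calculation. If the claim stands, a non-significant T2D/ASCVD result could be read as coming from a comparison with an 80% chance of finding the design effect, when that chance was about one in two.

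**Working it through.** **Inputs (all from the protocol).** p1 = 0.15, p2 = 0.30, alpha = 0.05, power 80%, loss 20 to 25%, allocation 1:1:1, T2D/ASCVD patients = 250. Whether alpha is one- or two-sided is not stated. Two-sided reproduces the printed figure, whereas one-sided would give 95 per arm.

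**1. Reproduce 121.** Two proportions, pooled variance under the null, no continuity correction:

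n = [z(0.975)·√(2·p̄·q̄) + z(0.80)·√(p1q1 + p2q2)]² / (p2 − p1)²

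- p̄ = 0.225, so √(2 × 0.225 × 0.775) = √0.34875 = 0.5906
- √(0.1275 + 0.21) = √0.3375 = 0.5809
- n = (1.960 × 0.5906 + 0.8416 × 0.5809)² / 0.0225 = 2.711 / 0.0225 = 120.5, rounded up to **121**

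At 90% power the same formula gives 161, also as printed.

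**2. Inflate for loss.**

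- Per arm: 121/0.80 = 151.3, so 152; 121/0.75 = 161.3, so 162
- In total: 363/0.80 = 453.8, so 454; 363/0.75 = 484 (456 to 486 if rounded up per arm)

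Reaching 750 from 363 would need a loss of 1 − 363/750 = 52%.

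**3. What 250 patients provide.** 250/3 = 83.3 per arm; × 0.80 = 66.7; × 0.75 = 62.5.

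**4. Power at those sizes.** Power = Φ{[0.15·√n − 1.960 × 0.5906] / 0.5809}

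| Evaluable per arm | Loss | Power, 15% vs 30% | Difference detectable at 80% power |
|---|---|---|---|
| 83.3 | none | 64% | 18.5 points |
| 66.7 | 20% | 55% | 21.0 points |
| 62.5 | 25% | 52% | 21.8 points |
| 121 | as required | 80% | 15 points |

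If alpha were one-sided, power after loss would still be only 64 to 67%.

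**5. The secondary comparison.** The figures above also apply to arm 1 against arm 2 if arm 2 reaches 30%, as the text and the bold table row say. However, that row prints 424 per arm for 1 vs 2 (80% power), and the formula returns 424 for 15% against 22.5%, not 30%. At 22.5%, power with 250 T2D/ASCVD patients is about 19 to 20% after loss. The claim for the secondary comparison fails on either reading.

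**6. Treatment-naïve restriction (illustration only).** The endpoint counts treatment-naïve patients. The T2D/ASCVD exclusion, read literally, removes only patients on both classes, so a patient on one class can be enrolled without being evaluable. If, as an assumption, 15% of those enrolled were in that position, evaluable numbers would be 66.7 × 0.85 = 56.7 and 62.5 × 0.85 = 53.1 per arm, with power 48% and 46%. The conclusion does not depend on this.

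**The case against.** **Comorbidity overlap.** Patients may count in more than one cohort, which is why the cohorts sum to more than 750. But 250 already counts every planned T2D/ASCVD patient, whatever else they have. Overlap adds none.

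**The calculation may be for the whole trial.** The sentence giving 15% speaks of eligible patients without naming T2D/ASCVD, and SGLT2i is also a counted class in both heart failure cohorts. If all 750 contributed, 187.5 to 200 per arm after loss would give 94 to 95% power. This is a fair caution against saying that other patients add nothing to the overall composite. It does not rescue the sentence at issue, which claims power for T2D/ASCVD by name. The Type 2 Diabetes Mellitus background section also gives 10 to 15% uptake of these classes in T2D.

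**Enrolment runs until each arm meets its targets.** The Randomization Scheme says so, but no T2D/ASCVD target above 250 is given.

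**Not every lost patient leaves the analysis.** Informed Consent and Withdrawal criteria keep patients in their randomized arm by intention to treat after consent is withdrawn or a clinician opts out. If few are excluded, power approaches 64%. That stands as the upper end and is still well short of 80%. The 52 to 55% range uses the protocol's own loss allowance.

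**It is a subanalysis.** True: the primary objective is the composite over all disease states, which this shortfall does not directly touch. The error is in an affirmative statement about T2D/ASCVD.

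**Conclusion.** The concern holds. The protocol needs 363 evaluable T2D/ASCVD patients and plans to enrol 250, of whom 187.5 to 200 would remain after its own stated loss, a shortfall of 45 to 48%. Power for 15% against 30% is 52 to 55% after loss and 64% with none. The total of 750 is not the result of inflating 121 per arm for 20 to 25% loss.

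This rests on a two-sided 0.05 test (the version that reproduces 121), even allocation of T2D/ASCVD patients over the arms, and no adjustment for two comparisons. Splitting alpha between the two comparisons, which the protocol does not propose, would lower power after loss to about 41 to 43%. The heart failure half of the claim is not assessed here.

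**What to change.** In Power Estimates:

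1. Delete the claim that the study is powered for T2D/ASCVD, for both the primary and the secondary comparison.
2. State what 250 T2D/ASCVD patients give for arm 1 against arm 3: about 52 to 55% power for 15% against 30% after 20 to 25% loss (64% with no loss), or 80% power for a difference of about 21 to 22 points after loss.
3. State the arm 2 rate behind the secondary comparison, and give its power on that rate.
4. Replace the sentence that derives 750. Either give the total that follows from 121 per arm (about 454 to 484 T2D/ASCVD patients) and say that the planned cohort does not reach it, or say that 750 was set on other grounds.
5. State the sidedness of alpha.

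This costs only wording in the protocol, carried into the SAP, and a less favourable stated power. It needs no extra patients. If the sponsor prefers to keep the claim of 80% power for the primary comparison, the T2D/ASCVD target has to rise to about 454 to 484, which does cost recruitment. Reporting the T2D/ASCVD subanalysis mainly as a difference with a 95% confidence interval would suit the planned size, but that is optional.

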## Intervention

Patients Randomized – 3 Quality Improvement Arms				
Arm	Duration	Surveys	Primary Outcome	Secondary Outcome
Teaching - CardioSmart Resources + Clinician Education	9 months	Patient perception QOL	GDMT baseline to 9 month change in average composite end-point of receiving the main classes of drugs (50% or higher of target doses for HF) among eligible patients	QOL Individual drug improvements Patient perception Cost/cost effectiveness
Technology - Facilitated Solution (Existing Team)				
Teams - Protocol-Supported Team, (Virtual GDMT Team)				

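### The protocol claims power in T2D/ASCVD, but 250 planned patients give about 83 per arm against its own requirement of 121; for combined HF the claim rests on no calculation

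*Protocol*

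**What the plan says.** The Intervention table in the protocol gives the primary outcome as "GDMT baseline to 9 month change in average composite end-point of receiving the main classes of drugs", with 50% or more of target dose required in HF. The Primary Objective section repeats this for the drug classes relevant to each disease state.

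The sample size under Statistical Methods, Power Estimates, starts from one component of that outcome: "Current estimates of use of either SGLT2i or GLP-1RA among eligible patients is 15" per cent. On an absolute difference of 15 points, "we would require 121 patients in each of the 3 arms to show 80% power". The table below it is headed "Rates of Primary Endpoint Over 9 months". Its bold row prints rates of 0.15, 0.3 and 0.3 for arms 1, 2 and 3, with 424 (80% power) and 568 (90%) per arm for 1 vs 2, and 121 and 161 for 1 vs 3.

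For HFrEF the section gives a 2% rate of optimal therapy and adds: "The differences for each arm are expected to be greater than the SGLT2i or GLP-1RA classes". For HFpEF it says: "Given the evolving evidence for HFpEF, there are no established rates for GDMT". For AF it does not expect to reach power. It makes arm 1 vs 3 the primary comparison and 1 vs 2 the secondary one, and then states: "The study will be powered for both primary and secondary comparisons for T2D/ASCVD and HF (HFrEF and HFpEF combined").

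The Population section sets the cohort sizes: "750 total with comorbidity overlap (250 HFrEF, 250 HFpEF, 500 AF, 250 T2D/ASVD").

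**The concern.** The power statement covers two disease groups and two comparisons, and each part can be checked against the protocol's own figures. The T2D/ASCVD part needs 121 per arm, while the planned cohort divided by three is well below that. The secondary comparison carries two incompatible inputs in one table row. The HF part covers HFrEF and HFpEF together, yet the same section says that no HFpEF rate exists.

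A reader who takes the statement at face value will treat a null T2D/ASCVD result as coming from a comparison with 80% power. If the true power is nearer one half, such a result says little about whether the strategies work. The table heading adds to the risk, because it presents rates for one component as rates for the whole primary outcome.

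**Working it through.** **Inputs.** Alpha 0.05, power 80% or 90%, rates 0.15 and 0.30, and loss of 20-25% come from Power Estimates. Allocation of 1:1:1 is from Research Methods, and the cohort sizes are from Population. Sidedness is not stated; two-sided is inferred below.

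**Formula.** Two proportions, pooled variance under the null, no continuity correction:

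n = [z(1−α/2)·√(2p̄(1−p̄)) + z(power)·√(p1(1−p1) + p2(1−p2))]² / (p2−p1)²

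**Step 1: reproduce 121.** p̄ = 0.225.
- √(2 × 0.225 × 0.775) = 0.5906.
- √(0.1275 + 0.2100) = 0.5809.
- n = (1.960 × 0.5906 + 0.8416 × 0.5809)² / 0.15² = 2.711 / 0.0225 = 120.5, so 121. At 90% power it is 161.

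Both match the table. The variants do not match 121: one-sided gives 95, a continuity correction gives 134, and alpha 0.025 gives 147. So the 121 is a two-sided binary comparison of SGLT2i/GLP-1RA use.

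**Step 2: T2D/ASCVD, arm 1 vs 3, at the planned size.** 250/3 = 83.3 per arm. After loss this is 83.3 × 0.80 = 66.7 or 83.3 × 0.75 = 62.5. Power = Φ{[0.15√n − 1.960 × 0.5906] / 0.5809}.

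| Per arm | Power, 15% vs 30% | Difference from 15% detectable at 80% power |
|---|---|---|
| 83.3 (no loss) | 64% | 18.5 points |
| 66.7 (20% loss) | 55% | 21.0 points |
| 62.5 (25% loss) | 52% | 21.8 points |

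Keeping 121 evaluable per arm would take 121/0.80 = 151.25, rounded up to 152 (456 in all), or 121/0.75 = 161.3, rounded up to 162 (486 in all), against 250 planned.

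**Step 3: arm 1 vs 2.** With arm 2 at the printed 0.3, the formula gives 121 and 161, the same as 1 vs 3. With arm 2 at 0.225, p̄ = 0.1875:
- n = (1.960 × 0.5520 + 0.8416 × 0.5494)² / 0.075² = 2.385 / 0.005625 = 424. At 90% power it is 568.

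So the printed sample sizes belong to 0.225. The other three rows of the table reproduce exactly as printed. At 15% vs 22.5%, T2D/ASCVD power is 23.5% with 83.3 per arm, 20% with 66.7 and 19% with 62.5. If 0.3 is the intended rate, the figures in step 2 apply to 1 vs 2 as well.

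**Step 4: HF.** The only HF inputs are a 2% HFrEF rate and an expectation of larger differences. If that is read as 2% vs 17% (an assumed 15-point difference), 59 per arm are needed. The 250 HFrEF patients leave 62.5 to 66.7 per arm after loss, with 82% to 85% power. At a 10-point difference the power is 59% to 62%.

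For HF combined, 500/3 = 166.7 per arm, or 125 to 133.3 after loss. No control rate is given, so a range is shown at an assumed 15-point difference:

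| Assumed control rate | Power after 20-25% loss |
|---|---|
| 5% | 95-96% |
| 15% | 81-84% |
| 30% | 69-72% |
| 40% | 66-69% |

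For the composite change across disease states, the protocol gives neither a rate nor a spread to compute from.

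**The case against.** **The trial enrols 750, so each arm has 250, well above 121.** This would answer the point if the power claim concerned all patients. It names T2D/ASCVD as a disease group, and that group is planned at 250 in total. Overlap between diseases does not help, because the 250 already counts patients who have other conditions too. For 1 vs 2 at 22.5%, even 250 per arm would give only 58% power, or 46% to 49% after loss.

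**The randomization scheme keeps enrolment open until every arm has met its accrual targets, expressly for the sake of power.** This is a fair point, and accrual could run past 250. But no T2D/ASCVD target above 250 is stated, so the rule softens the shortfall without removing it.

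**The HF claim is not baseless.** This stands in part. A reader might infer that nothing in the protocol supports it, but there is a 2% HFrEF rate and an expected difference larger than that for SGLT2i/GLP-1RA. On a 15-point reading, HFrEF alone would be adequately powered. What is missing is support for the claim as made, for HFrEF and HFpEF combined. The 2% also refers to optimal therapy, whereas the HFrEF composite counts drug classes at 50% or more of target dose.

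**The table heading is not plainly wrong.** This also stands in part. SGLT2i and GLP-1RA are the T2D/ASCVD drug classes within the primary outcome, so the rates belong to a component of it and not to a foreign endpoint. The heading needs a qualifier only.

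**Conclusion.** The power statement is wrong as written for T2D/ASCVD. At the planned 250 patients, power for 15% vs 30% is 64% before loss and 52% to 55% after it, not 80%. For 1 vs 2 the bold row contradicts itself; if its sample sizes stand, T2D/ASCVD power is 23.5% before loss and 19% to 20% after. For combined HF and for the composite change, the protocol offers no rate, difference or sample size that supports a claim. Plausible assumptions put combined-HF power anywhere from 66% to 96%.

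These figures assume a two-sided 0.05 test, an even split of each cohort over the arms, enrolment of exactly the planned cohort sizes, and, for HF, no overlap between the HFrEF and HFpEF cohorts. T2D/ASCVD power is higher if accrual exceeds 250.

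A reader might go further and infer that 750 patients are too few for the composite primary outcome, or that the HF comparison is underpowered. The protocol supports neither inference: it gives no basis for judging the first, and the second depends on a control rate that it does not state.

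**What to change.** In Power Estimates:
- Restate T2D/ASCVD power at 250 patients with the 20-25% loss applied to that cohort, for 1 vs 3 and for 1 vs 2. If a larger T2D/ASCVD accrual target is intended, state it.
- Reconcile the bold row, so that the arm 2 rate and the sample sizes for 1 vs 2 agree.
- Qualify the table heading as the SGLT2i/GLP-1RA (T2D/ASCVD) component of the primary outcome.
- For HFrEF and HFpEF combined, and for the composite change, either give power at the planned size with its assumptions or say that the trial was not sized on them. Qualify the HF power claim to match.

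This costs protocol wording and a few calculations, with no burden on patients or data collection. The downside is that the sponsor must state less favourable power figures.

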### Quality Control

TRANSFORM collaborators have established a robust plan for ensuring appropriate and commercially reasonable physical, technical, and administrative safeguards are in place to maintain the integrity of study data stored and used.

All study data shall be maintained on secure servers with appropriate safeguards in place. The ACCF project team will periodically review all activities involving Protected Health Information to ensure that such safeguards including standard operating procedures are being followed. The

partners shall also communicate to all study personnel the procedure for notifying the ACCF of any breach of confidentiality and immediate mitigation standards that need to be followed.

ACCF shall limit access to Protected Health Information, and to equipment, systems, networks, applications and media that contain, transmit, process or store Protected Health Information (“Equipment, Systems and Media”), to those employees of ACCF who need to access the Protected Health Information for purposes of performing ACCF’s obligations to Covered Entities (“Participants”) who are in a contractual relationship with the ACCF. ACCF shall implement discretionary access controls designed to permit each user access to Equipment, Systems and Media, which are specifically necessary to accomplish only assigned tasks on behalf of study participants. ACCF shall strictly control physical and electronic access to Equipment, Systems and Media in the following manner:

